8. PHARMACEUTICAL INFORMATION

A list of the adverse events and potential risks associated with the investigational agent administered in this study can be found in Section 10.1.

8.1 Telaglenastat (CB-839) HCl

8.1.1 Telaglenastat (CB-839) HCl (NSC# 795998)

Chemical Name: N-[5-[4-[6-[[2-[3-(trifluoromethoxy)phenyl]acetyl]amino]-3-pyridazinyl]butyl]-1,3,4-thiadiazol-2-yl]-2-pyridineacetamide

Classification: Glutaminase Inhibitor

Molecular Formula: C₂₆H₂₄F₃N₇O₃S **M.W.:** 571.57

Mode of Action: Telaglenastat (CB-839) HCl is a potent and selective reversible inhibitor of glutaminase activity. It is an allosteric and noncompetitive inhibitor of both GAC (“glutaminase C”) and KGA (“kidney glutaminase”) isoforms of glutaminase (GLS), but does not inhibit glutaminase-2.

How Supplied: Telaglenastat (CB-839) HCl is supplied as 200 mg white to off-white oval coated tablets. Each tablet contains 200 mg Telaglenastat (CB-839) HCl salt which is equivalent to 188 mg of Telaglenastat (CB-839) free base. Tablet excipients include microcrystalline cellulose, lactose monohydrate, sodium starch glycolate, magnesium stearate, and Opadry II White (coating). The approximate dimensions (L x W x H) are 14.5 mm x 6.9 mm x 6.0 mm (0.57" x 0.273" x 0.236"). Each 50-count bottle is sealed with a tamper-evident seal and a child-proof cap. Tablets can be transferred to another bottle per institutional procedure prior to dispensing.

In late 2021 PMB will transition to a new formulation of telaglenastat (CB-839) HCl. This new telaglenastat (CB-839) HCl formulation is supplied as 200 mg purple, oval, coated tablets embossed with the letters “TEL” on one side of the tablet. Each tablet contains 200 mg CB-839 HCL salt which is equivalent to 188 mg of CB-839 free base. Tablet excipients include microcrystalline cellulose, lactose monohydrate, sodium starch glycolate, magnesium stearate, and Opadry® II 85F90035 Purple (coating). This color is free from potentially allergenic dyes and is an approved color for US and EU markets. The approximate dimensions (L x W x H) are 14.5 mm x 6.9 mm x 6.0 mm (0.57" x 0.273" x 0.236").

Each 240-count bottle is sealed with a tamper-evident seal and a child-proof cap. The packaging consists of white opaque high-density polyethylene (HDPE) plastic bottles closed with a child resistant cap (CRC) and sealed with a tamper-evident induction seal. No rayon in bottle. Tablets can be transferred to another bottle per institutional procedure prior to dispensing.

Storage: Store at room temperature (20°C-25°C). Excursions +/- 5°C are permitted. If a storage temperature excursion is identified, promptly return Telaglenastat (CB-839) HCl to (20°C-25°C) and quarantine the supplies. Provide a detailed report of the excursion (including documentation of temperature monitoring and duration of the excursion) to [contact] for determination of suitability.

Stability: Stability studies are ongoing.

Route of Administration: Oral, approximately 12 hours apart, with food. Administer the first dose immediately after breakfast, the second dose approximately 12 hours later. Doses should be taken at approximately the same times each day. Missed doses may be taken if it is not more than three hours past the scheduled administration time for the missed dose. Vomited doses should not be made up.

Metabolism: In *in vitro* studies, Telaglenastat (CB-839) HCl is metabolized by amide hydrolysis and to a lesser extent, P450-mediated hydroxylation.

Potential Drug Interactions: In *in vitro* data, Telaglenastat (CB-839) HCl is a weak *o* inhibitor of CYP2C9; therefore, concomitant medications that are metabolized by CYP2C9 should either be given with caution (including closely monitoring for signs of toxicity or altered efficacy) or substituted with a non-CYP2C9 substrate. Telaglenastat (CB-839) HCl is not an inhibitor of CYP1A2, CYP2B6, CYP2C8, CYP2C19, CYP2D6, and CYP3A4 nor an inducer of CYP1A2, CYP2B6, and CYP3A4.

Telaglenastat (CB-839) HCl requires low pH conditions for optimal solubilization. Concomitant use of proton pump inhibitors (PPIs) should be avoided due to significantly reduced exposure to Telaglenastat (CB-839) HCl. Patients may be switched to shorter acting agents such as histamine H₂ receptor antagonists (H₂RA) and as-needed antacid buffering agents (e.g. calcium carbonate, magnesium hydroxide and aluminum hydroxide) since, based on limited clinical data, they do not appear to result in a significant reduction of Telaglenastat (CB-839) HCl exposure. It is recommended that Telaglenastat (CB-839) HCl be dosed at least 2 hours before or at least 2 hours after antacid therapy.

Patient Care Implications: Women of child-bearing potential must have a negative pregnancy test prior to starting Telaglenastat (CB-839) HCl and use two forms of effective birth control while receiving Telaglenastat (CB-839) HCl.

Availability

Telaglenastat (CB-839) HCl is an investigational agent supplied to investigators by the Division of Cancer Treatment and Diagnosis (DCTD), NCI.

Telaglenastat (CB-839) HCl is provided to the NCI under a Collaborative Agreement between the Pharmaceutical Collaborator and the DCTD, NCI (see Section 13.4).

8.1.2 Agent Ordering and Agent Accountability

8.1.2.1 NCI-supplied agents may be requested by eligible participating Investigators (or their authorized designee) at each participating institution. The CTEP-assigned protocol number must be used for ordering all CTEP-supplied investigational agents. The eligible participating investigators at each participating institution must be registered with CTEP, DCTD through an annual submission of FDA Form 1572 (Statement of Investigator), NCI Biosketch, Agent Shipment Form, and Financial Disclosure Form

(FDF). If there are several participating investigators at one institution, CTEP-supplied investigational agents for the study should be ordered under the name of one lead participating investigator at that institution.

Sites may order initial agent supplies when a subject is being screened for enrollment onto the study.

Submit agent requests through the PMB Online Agent Order Processing (OAOP) application. Access to OAOP requires the establishment of a CTEP Identity and Access Management (IAM) account and the maintenance of an “active” account status, a “current” password, and active person registration status. For questions about drug orders, transfers, returns, or accountability, call or email PMB any time. Refer to the PMB’s website for specific policies and guidelines related to agent management.

8.1.2.2 Agent Inventory Records – The investigator, or a responsible party designated by the investigator, must maintain a careful record of the receipt, dispensing and final disposition of all agents received from the PMB using the appropriate NCI Investigational Agent (Drug) Accountability Record (DARF) available on the CTEP forms page. Store and maintain separate NCI Investigational Agent Accountability Records for each agent, strength, formulation and ordering investigator on this protocol.

8.1.3 Investigator Brochure Availability

The current versions of the IBs for the agents will be accessible to site investigators and research staff through the PMB OAOP application. Access to OAOP requires the establishment of a CTEP IAM account and the maintenance of an “active” account status, a “current” password, and active person registration status. Questions about IB access may be directed to the PMB IB Coordinator via email.

9. STATISTICAL CONSIDERATIONS

9.1 Study Design/Endpoints

Primary Endpoint:

1. Best overall response rate (BORR) based on RECIST V1.1 achieved by 6 months of CB-839 HCl treatment in specific pathway aberrant tumors (MPNST, NF1, KEAP1/NRF2 & STK11/LKB1)

This will be a basket trial that will enroll patient in four different basket cohorts with specific pathway aberrant tumors.

Cohort (Basket) 1: *NF1* mutant malignant peripheral nerve sheath tumors (MPNST)

Cohort (Basket) 2: *NF1* mutant other cancers

Cohort (Basket) 3: *KEAP1/NRF2* mutant cancers

Cohort (Basket) 4: *STK11/LKB1* mutant cancers

Within each cohort, we will employ an optimal Simon two-stage design. Specifically, within each cohort, *we will enroll 9 patients, and if 0 respond*, the study will be stopped early for futility within that cohort. Otherwise, an additional 18 patients will be enrolled, and if there are 4 or more responses out of the total sample of 27 patients, we will conclude that the treatment is worthy of further consideration within that cohort.

This design has an overall type-I error rate of 5% (one-sided) within each cohort, and provides 88% power to reject the null hypothesis that the response rate is 0.05 when the true response rate is 0.25. Within a given cohort, this design has a 63% chance of stopping early and an expected total enrollment of 15.7 patients under the null hypothesis (i.e. if the true response rate were 0.05).

9.2 Sample Size/Accrual Rate

We plan to accrue about 108 patients in this study (up to 27 patients per cohort). It is anticipated that 2-4 patients may be enrolled per month onto this study. It is expected that 18-30 months will be required to accrue the number of patients necessary to complete the trial.

PLANNED ENROLLMENT REPORT

Racial Categories	Ethnic Categories				Total
	Not Hispanic or Latino		Hispanic or Latino		
	Female	Male	Female	Male	
American Indian/ Alaska Native	0	0	9	9	18
Asian	5	4	5	4	18

Racial Categories	Ethnic Categories				Total
	Not Hispanic or Latino		Hispanic or Latino		
	Female	Male	Female	Male	
Native Hawaiian or Other Pacific Islander	0	0	0	0	0
Black or African American	9	9	9	9	36
White	9	9	9	9	36
More Than One Race	0	0	0	0	0
Total	23	22	32	31	108

PHS 398 / PHS 2590 (Rev. 08/12 Approved Through 8/31/2015)

OMB No. 0925-0001/0002

9.3 Analysis of Secondary Endpoints

Secondary Endpoint:

1. Safety, progression free survival (PFS), time to progression (TTP) and overall survival (OS).

We will tabulate toxicity by cohort, type, severity and attribution. For patients with objectively measurable disease, as defined by RECIST v1.1, progression-free survival (PFS), time to progression (TTP), and overall survival (OS) will be calculated. We will estimate PFS and OS using the Kaplan-Meier method with time zero set to C1D1. OS is defined as time to death from any cause and PFS is defined as time to progression or death whichever comes first. OS is censored in patients not known to be dead at the time they were last known to be alive and PFS is censored in patients alive and progression-free at the date of last clinical follow-up. We will estimate the medians and select probabilities along with 95% confidence intervals. TTP will be estimated in a similar fashion and is defined as time to progression starting at C1D1. If more than a handful of patients die without progression, we will use Aalen-Johansen estimates to adjust for the competing risk of death.

2. Overall response rate and clinical benefit rate (CR, PR and SD > 12 weeks of Telaglenastat (CB-839) HCl)

Ho: CB 839 - Response Rate (RR) in disease	Ha: Target RR of combination in disease	Calculation	Statistic & Significance	Responsible investigator
5 %	25 %	ORR = pre-therapy sum longest diameters (5 or less lesions) / post-therapy sum longest diameters (same 5 or less lesions)	It is a one-sample binomial test with alpha = 5%.	[name]

3. Pharmacodynamic tumor oncometabolite levels of glutamine, glutamate, and aspartate between 0 and 8 hours post- Telaglenastat (CB-839) HCl dose among patients with persistent or recurrent metastatic cancers.

We will assess PD changes before and after treatment using the Wilcoxon signed rank test. For normally distributed data, with 27 patients we can detect a standardized mean difference (mean difference divided by standard deviation of differences) = 0.6 with 85% power assuming a two-sided 5% alpha. We will correlate these changes with response to treatment using Wilcoxon rank sum test. We will also perform a ROC curve analysis. With 27 patients, if the response rate is roughly 50%, we can detect an area under the ROC curve = 0.83 as significantly higher than 0.5 (the null value) with 85% power assuming a 5% alpha.

Assuming 20 patients have data, we will have 85% power to detect a standardized effect size of 0.706 using a paired t-test and we can detect an area under the ROC curve of 0.887. Assuming 15 patients have data, we will have 85% power to detect a standardized effect size of 0.832 using a paired t-test and we can detect an area under the ROC curve of 0.947.

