1.2 Secondary Objectives

- 1.2.1 To determine the safety, PFS, TTP and OS.
- 1.2.2 To determine the ORR (highest objective response achieved between start of therapy and progression), TTR and CBR of Telaglenastat (CB-839) HCl
- 1.2.3 Correlative Objectives: To assess pharmacodynamic changes and adaptive responses and correlate with response to treatment as well as disease progression

1.3 Exploratory objectives:

- 1.3.1 Correlate ¹⁸F-FDG PET/CT pre-therapy and 8-weeks post-therapy response to Telaglenastat (CB-839) HCl therapy
- 1.3.2 Evaluate changes in level of circulating tumor DNA at baseline, one month on-treatment and time of progression (MoCHA Labs) to treatment response.
- 1.3.3 Quantify the peripheral blood concentrations of the metabolites: Aspartate, Glutamate, Glutamine and Arginine (@Mayo clinic Oncometabolomics core) and correlate with response.
- 1.3.4 Evaluate the PD effect of Telaglenastat (CB-839) HCl on systemic levels of the TCA cycle metabolites in peripheral blood (baseline and one month) as part of the protocol.
- 1.3.5 Evaluate tumor by Reverse phase protein array (@core facility at MD Anderson) and RNA seq to evaluate changes from pre-treatment, during treatment and post treatment specimens.
- 1.3.6 Perform PDX modelling-co-clinical trials (@[name] lab MD Anderson) to understand response / resistance mechanisms and also evaluate combination therapies for future development.

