6. TREATMENT PLAN

6.1 Agent Administration

Treatment will be administered on an outpatient basis. Reported adverse events and potential risks are described in Section 10. Appropriate dose modifications are described in Section 7. No investigational or commercial agents or therapies other than those described below may be administered with the intent to treat the patient's malignancy.

This phase 2 basket clinical trial utilizes single agent CB 839 HCl at the recommended phase 2 dose at 800 mg (Table 2 and 3).

Table 2. Treatment Plan for Telaglenastat (CB-839) HCl as a single agent	
Category	Treatment Plan
Telaglenastat (CB-839) HCl agent dose	800 mg
Telaglenastat (CB-839) HCl administration and schedule	Telaglenastat (CB-839) HCl dose by mouth twice daily, approximately 12 hours apart, immediately after a meal on day 1 to day 28, repeated every 28 days
Duration of treatment	Repeated every 28 days until unacceptable toxicity or disease progression. Refer to Section 6.3 for additional stopping criteria.
Duration of the study	Upon completion of follow-up procedures.
Duration of follow-up	Every 3 months (\pm) 14 days after the last administered treatment dose

If patient develop toxicity then the dose can be reduced as per Table 3.

Table 3. Dose Reductions of Telaglenastat (CB-839) HCl	
Dose Level	Telaglenastat (CB-839) - HCl Dose

Starting dose	800 mg BID
First dose reduction	600 mg BID
Second dose reduction	400 mg BID
Third dose reduction	Discontinue Telaglenastat (CB-839) HCl

The patient will be requested to maintain a medication diary of each dose of medication. The medication diary will be returned to clinic staff at each clinic visit.

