9.4.2 Evaluation of Response

All patients who receive at least one dose of study drug are evaluable for response. Patients who are enrolled but who do not receive any study drug may be replaced.

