Target lesions. All measurable lesions up to a maximum of 2 lesions per organ and 5 lesions in total, representative of all involved organs, should be identified as **target lesions** and recorded and measured at baseline. Target lesions should be selected on the basis of their size (lesions with the longest diameter), be representative of all involved organs, but in addition should be those that lend themselves to reproducible repeated measurements. It may be the case that, on occasion, the largest lesion does not lend itself to reproducible measurement in which circumstance the next largest lesion which can be measured reproducibly should be selected. A sum of the diameters (longest for non-nodal lesions, short axis for nodal lesions) for all target lesions will be calculated and reported as the baseline sum diameters. If lymph nodes are to be included in the sum, then only the short axis is added into the sum. The baseline sum diameters will be used as reference to further characterize any objective tumor regression in the measurable dimension of the disease.

Non-target lesions. All other lesions (or sites of disease) including any measurable lesions over and above the 5 target lesions should be identified as **non-target lesions** and should also be recorded at baseline. Measurements of these lesions are not required, but the presence, absence, or in rare cases unequivocal progression of each should be noted throughout follow-up.

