12.1.4 Response Criteria

12.1.4.1 Evaluation of Target Lesions

Complete Response (CR): Disappearance of all target lesions. Any pathological lymph nodes (whether target or non-target) must have reduction in short axis to <10 mm (<1 cm).

Partial Response (PR): At least a 30% decrease in the sum of the diameters of target lesions, taking as reference the baseline sum diameters.

Progressive Disease (PD): At least a 20% increase in the sum of the diameters of target lesions, taking as reference the smallest sum on study (this includes the baseline sum if that is the smallest on study). In addition to the relative increase of 20%, the sum must also demonstrate an absolute increase of at least 5 mm (0.5 cm). (Note: the appearance of one or more new lesions is also considered progressions).

Negative FDG-PET at baseline, with a positive FDG-PET at follow-up is a sign of PD based on a new lesion. No FDG-PET at baseline and a positive FDG-PET at follow-up: If the positive FDG-PET at follow-up corresponds to a new site of disease confirmed by CT, this is PD. If the positive FDG-PET at follow-up is not confirmed as a new site of disease on CT, additional follow-up CT scans are needed to determine if there is truly progression occurring at that site (if so, the date of PD will be the date of the initial abnormal FDG-PET scan). If the positive FDG-PET at follow-up corresponds to a pre-existing site of disease on CT that is not progressing on the basis of the anatomic images, this is not PD. (Note: A 'positive' FDG-PET scan lesion means one which is FDG avid with an uptake greater than twice that of the surrounding tissue on the attenuation corrected image.)

Stable Disease (SD): Neither sufficient shrinkage to qualify for PR nor sufficient increase to qualify for PD, taking as reference the smallest sum diameters while on study.

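### Section 9.3 defines the secondary ORR as a within-patient ratio of tumour sums, which the binomial test of 5% versus 25% in the same row cannot use

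*Combined protocol and SAP*

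**What the plan says.** Item 2 of Section 9.3 covers the overall response rate and the clinical benefit rate. One table row carries the specification:

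- Null response rate 5%, target response rate 25%. The target column is headed "Ha: Target RR of combination in disease".
- Calculation: "ORR = pre-therapy sum longest diameters (5 or less lesions) / post-therapy sum longest diameters (same 5 or less lesions".
- Test: "It is a one-sample binomial test with alpha = 5" per cent. The row gives neither a sample size nor the sidedness.

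Other sections bear on the same endpoint:

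- Section 1.2 describes ORR as the "highest objective response achieved between start of therapy and progression".
- Section 9.4.2 sets the population: "All patients who receive at least one dose of study drug are evaluable for response".
- Section 12.1.2 on target lesions: "If lymph nodes are to be included in the sum, then only the short axis is added into the sum".
- Section 12.1.4.1 defines partial response on target lesions as "At least a 30% decrease in the sum of the diameters of target lesions, taking as reference the baseline sum diameters". It counts new lesions as progression and measures progression from the smallest sum on study.
- Section 12.1.4.3 assigns the best overall response from target lesions, non-target lesions and new lesions together, and requires confirmation in this study.
- Section 6.1: "This phase 2 basket clinical trial utilizes single agent CB 839 HCl".

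**The concern.** A one-sample binomial test needs a number of responders out of a number of patients. The Calculation cell supplies a positive continuous ratio for each patient and calls it ORR. The two entries stand in the same row and cannot both be followed.

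ORR up to progression is a named secondary objective, distinct from the primary BORR by 6 months, and this row is the only place where the statistical section says how to calculate it. Anyone programming from Section 9.3 must either compute something the test cannot take or set the written formula aside and rebuild the definition from other sections. A final report that departs from its own stated formula invites questions that are easily avoided.

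Separately, the target column speaks of a combination although the trial is single-agent. That is a slip of wording with no numerical effect.

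**Working it through.** **1. The design figures in Section 9.1, which use responder counts.** Inputs: stop at 0 of 9; otherwise enrol 18 more and succeed at 4 or more of 27; rates 0.05 and 0.25.

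P(reject) = Σ over x = 1 to 9 of P(Bin(9, p) = x) × P(Bin(18, p) ≥ max(0, 4 − x)).

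| Quantity | Stated | Recomputed |
|---|---|---|
| Power at 0.25 | 88% | 0.881 |
| Type I error at 0.05 | 5% | 0.0369, within the nominal 5% |
| Early stop at 0.05 | 63% | 0.95^9 = 0.630 |
| Expected N at 0.05 | 15.7 | 9 + 18 × (1 − 0.630) = 15.66 |

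The 5% and 25% in the Section 9.3 row are the same two rates, and they make sense only as proportions of patients.

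**2. What the Calculation cell yields.** Ratio = baseline sum / post-therapy sum = 1 / (1 + fractional change).

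| Change from baseline | Ratio |
|---|---|
| 50% decrease | 1/0.50 = 2.00 |
| 30% decrease (PR threshold) | 1/0.70 = 1.43 |
| None | 1.00 |
| 20% increase | 1/1.20 = 0.83 |

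A ratio of 0.05 means a post-therapy sum 1/0.05 = 20 times baseline; 0.25 means 1/0.25 = 4 times. The ratio therefore cannot be the quantity compared with 5% and 25%.

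**3. Could the ratio at least classify patients?** The tumour sizes here are assumed for illustration.

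- *New lesions.* Target sums of 100 then 60 mm give 100/60 = 1.67. This is so both for a patient with no new lesion and no non-target progression (PR at that scan) and for one with a new lesion at that scan (PD).
- *Choice of scan.* Sums of 100, 50, then 60 mm give 2.00 at the second scan and 1.67 at the third. The third is 20% and 10 mm above the smallest sum, so it is PD under Section 12.1.4.1. This patient could still count as a responder from the 50 mm scan if that response was confirmed. The cell does not say which scan applies.
- *Nodes.* A node goes from 30 × 16 mm to 24 × 11 mm. Longest diameters, as in the cell, give 30/24 = 1.25, a 20% decrease that misses PR. The short axis, as Section 12.1.2 requires, gives 16/11 = 1.45, a 31% decrease that meets it.
- *No value.* The ratio is undefined when the post-therapy sum is zero, for example when all target lesions are non-nodal and disappear. It is also missing for a dosed patient with no post-baseline scan, whom Section 9.4.2 counts as evaluable.

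**4. The same row on responder counts.** The row gives no n; take 27, the full cohort. For a single-stage test that rejects at 4 or more:

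P(X ≥ 4) = 1 − Σ over k = 0 to 3 of C(27, k) p^k (1 − p)^(27 − k) = 0.0437 at p = 0.05 and 0.933 at p = 0.25.

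A cut-off of 3 would give 0.150 at p = 0.05, so 4 is the right cut-off for a one-sided 5% test. With the stop at 0 of 9 included, the same rule gives 0.0369 and 0.881, as in step 1. Once ORR is a proportion, the row works.

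**The case against.** The strongest reply is that nobody would be misled. The row names a response rate, two percentages and a binomial test. Section 9.1 tests responder counts against the same percentages, and Sections 9.4.2 and 12.1.4 supply the population and the response rules. The cell may be shorthand for how tumour change is measured in each patient. No sample size, error rate or trial decision depends on it.

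Much of that stands, and it limits the weight of the point. It does not clear the cell. Even as shorthand, the formula is inverted relative to the RECIST rule, uses the wrong diameter for nodes, and leaves out new lesions, non-target lesions and confirmation.

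Three narrower objections are also fair:

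- The description in Section 1.2 is itself a per-patient quantity. It shows that a response category is intended but does not supply the numerator and denominator.
- A missing post-baseline scan would defeat a percent-change measure equally, so that gap is not peculiar to the ratio.
- The single-stage 0.933 is not the power of this trial. With the futility stop, 0.881 is the relevant figure.

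**Conclusion.** The Calculation cell is wrong as written: the quantity it labels ORR cannot enter the test beside it, and it conflicts with the protocol's own response rules. That conclusion rests on the text and on simple arithmetic. The lesion sizes are assumed, and so is n = 27 for the secondary test; neither is needed for it.

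The consequence is modest. One secondary endpoint has a definition that the analyst must override, and the intended one can be reconstructed from elsewhere in the protocol. The primary BORR, the Simon design, PFS, TTP and OS are untouched. It should be corrected before analysis, but it does not threaten the trial.

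**What to change.** Replace the Calculation cell with a definition such as:

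> ORR = number of patients whose best overall response from start of treatment to progression is CR or PR under RECIST 1.1 (Section 12.1.4.3), divided by all patients in that cohort who took any study drug.

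Report it by cohort with an exact 95% confidence interval. A dosed patient without a post-baseline scan then stays in the denominator and is not a responder; it is worth saying so explicitly.

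In the same edit:

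- State that the test is run per cohort and whether it is one-sided, as in Section 9.1. The distinction is visible in the results. With 4 of 27 responders the one-sided 5% test rejects, yet the two-sided exact 95% interval, 4.2% to 33.7%, includes 5%. That interval also takes no account of the two-stage stop.
- Change the target column so that it refers to telaglenastat and not to a combination.
- Give the clinical benefit rate, which shares the item heading, its own calculation.
- If tumour shrinkage is of interest, report best percent change from baseline separately as a descriptive measure.

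The core correction is two table cells in Section 9.3, and the other items add a line or two. No new data, visits or patients are needed.

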5. BIOMARKER, CORRELATIVE, AND SPECIAL STUDIES

5.1 Summary Table for Specimen Collection

Time Point	Specimen and Quantity	Send Specimens to:
Screening (Pre-treatment)		
	
 • 3-6 tissue cores in formalin¹ • 1 core snap-frozen • Optional: 1 core or FNA in media • 10 mL blood in purple top EDTA tube processed for plasma² • Optional: 20 mL blood in cfDNA Streck tubes² (2 x 10 mL) 	EET Biobank
Day 1		
Baseline / 0 hours (fasting) 0.5 Hours 1 Hours 2 Hours 4 Hours 8 Hours	
 • Frozen plasma processed from 3 mL blood in purple top EDTA tube at 6 collection times^{2,3} (For PK studies) 	[name] / Mayo Clinic Cancer Center (Mayo) Pharmacology Shared Resource
Baseline / 0 hours (fasting) 0.5 Hours 1 Hours 2 Hours 4 Hours 8 Hours	
 • 3 mL blood in purple top EDTA tube at each time point – processed for plasma at site^{2,3} (For oncometabolite studies) 	EET Biobank
Day 15		
Baseline / 0 hours (fasting) 0.5 Hours 1 Hours 2 Hours 4 Hours 8 Hours	
 • Frozen plasma processed from 3 mL blood in purple top EDTA tube at 6 collection times^{2,3} (For PK studies) 	[name] / Mayo Clinic Cancer Center (Mayo) Pharmacology Shared Resource
Baseline / 0 hours (fasting) 0.5 Hours 1 Hours 2 Hours 4 Hours 8 Hours	
 • 3 mL blood in purple top EDTA tube at each time point – processed for plasma at site^{2,3} (For oncometabolite studies) 	EET Biobank
Week 4 (C1D22 ± 3 days)		

	
• Optional: 3-6 tissue cores in formalin¹• Optional: 1 cores snap-frozen• Optional: 1 core or FNA in media• 10 mL blood in purple top EDTA tube processed for plasma after drug administration³• Optional: 20 mL blood in cfDNA Streck tubes² (2 x 10 mL)	EET Biobank
Week 8 (C2D22 ± 3 days)		
	
• Optional: 20 mL blood in cfDNA Streck tubes² (2 x 10 mL)	EET Biobank
Progression/Relapse		
	
• Optional: 3-6 tissue cores in formalin¹• Optional: 1 core snap-frozen• Optional: 1 core or FNA in media• Optional: 20 mL blood in cfDNA Streck tubes² (2 x 10 mL)	EET Biobank

¹A copy of the radiology and operative reports from the tissue removal procedure must be sent with the tissue to the EET Biobank. When completed, upload the corresponding pathology reports to Rave.

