²All “prior to drug administration” samples should be collected after at least 8 hours of fasting (the patient must not eat or drink anything but water).

³All “after drug administration” samples should be collected after patients are dosed with CB-839 HCl immediately after a meal.

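### The pharmacodynamic test does not name its before and after samples, and the same-day contrast that its 0–8 hour window suggests measures drug plus meal

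*Combined protocol and SAP*

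**What the plan says.** Section 9.3, item 3, defines the endpoint as "Pharmacodynamic tumor oncometabolite levels of glutamine, glutamate, and aspartate between 0 and 8 hours post" dose. (It says tumor levels, but the serial samples in sections 5.1 and 5.7 are plasma; that is a separate inconsistency.) The analysis sentence is "We will assess PD changes before and after treatment using the Wilcoxon signed rank test". No day and no pair of time points is named. The power statement reads "For normally distributed data, with 27 patients we can detect a standardized mean difference" of "0.6 with 85% power assuming a two-sided 5% alpha".

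The food state is set elsewhere. Footnote 2 of section 5.1 says that pre-dose "samples should be collected after at least 8 hours of fasting (the patient must not eat or drink anything but water"). Footnote 3 says that post-dose "samples should be collected after patients are dosed with CB-839 HCl immediately after a meal". Section 5.4.5.4 and footnote 10 of the study calendar (section 11) agree: fasted baseline first, then the dose with food, then samples at 0.5, 1, 2, 4 and 8 hours, on Days 1 and 15.

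Objective 1.3.4 concerns "TCA cycle metabolites in peripheral blood (baseline and one month"). In section 5.1 the screening tube carries the fasting footnote. The Week 4 tube is "10 mL blood in purple top EDTA tube processed for plasma after drug administration" and carries the fed footnote.

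Appendix D reads a rise in glutamine and a fall in glutamate and aspartate from baseline as effective inhibition.

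**The concern.** If before is the 0-hour sample and after is any sample from 0.5 to 8 hours on the same day, two things change together: the patient takes the drug and the patient eats. The analytes are amino acids, so a meal could plausibly move them. Every fed sample in the trial is also an on-drug sample, so no analysis of that contrast can separate the two sources. A meal shift in the drug's direction would look like target engagement, and a shift in the opposite direction would hide it. For 1.3.4, both candidate baselines (screening and Day 1 pre-dose) are fasted while Week 4 is fed, so the same problem arises. At stake is the interpretation of an integrated, mandatory biomarker.

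**Working it through.** **1. Plan's own figure.** Inputs from section 9.3: n = 27, standardized mean difference d = 0.6, two-sided alpha 5%. For a paired t-test the power comes from the noncentral t distribution with df = n − 1 = 26 and noncentrality d√n = 0.6 × √27 = 3.12. The result is 85.1%, against 85% stated. The reduced-sample cases also reproduce: n = 20, d = 0.706 gives 85.0%, and n = 15, d = 0.832 gives 85.0%. The signed-rank test named in the plan gives 83.5% by simulation for n = 27 and d = 0.6. The arithmetic is sound; the issue is what the paired difference estimates.

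**2. What each available contrast contains.**

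| Contrast | Before | After | Difference includes |
|---|---|---|---|
| Same day, 0 vs 0.5–8 h | fasted | fed, dosed | drug + meal |
| Screening vs Week 4 (1.3.4) | fasted | fed, dosed | drug + meal |
| Day 1 vs Day 15 pre-dose | fasted, untreated | fasted, on treatment | drug at trough, no same-day meal |

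**3. Sensitivity to a meal shift.** The documents give no meal effect on these metabolites; the 1.3-fold food effect in sections 2.2.4 and 6.1.1 concerns drug exposure. So the shift m, in SDs of the paired difference, is an assumption. With no drug effect, the rejection probability of the two-sided 5% test uses the formula in step 1 with d replaced by m:

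| m | m√27 | n = 27 | n = 20 | n = 15 | signed-rank simulation, n = 27 |
|---|---|---|---|---|---|
| 0 | 0 | 5% | 5% | 5% | 4.8% |
| 0.2 | 1.04 | 17.0% | 13.6% | 11.2% | 16.1% |
| 0.3 | 1.56 | 32.4% | 24.7% | 19.2% | 30.8% |
| 0.4 | 2.08 | 51.7% | 39.7% | 30.3% | 50.5% |

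In the other direction, a meal shift of 0.3 SD against a true drug effect of 0.6 SD leaves a net 0.3 SD, so power at n = 27 falls from 85.1% to 32.4%.

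**4. Rank-sum and ROC analyses.** Both depend only on the ordering of patients' change scores. Adding the same constant to every score leaves that ordering unchanged, so a common meal shift biases neither. Between-patient variation in meal response would only add noise.

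**5. Cost of the fasted pair.** If the effect at trough is still 0.6 SD, power at n = 27 stays at 85.1%. If it is 0.4 SD, power is 51.7%. A rough guide to the trough uses mean Cmax and Tmax from Table 1 (section 2.3), the 4-hour half-life, and C(12 h) = Cmax × 0.5^((12 − Tmax)/4):
- 800–1000 mg row (N = 5): 1.0 × 0.5^(9.2/4) ≈ 0.20 µg/mL
- 600 mg row (N = 48): 1.6 × 0.5^(7.8/4) ≈ 0.41 µg/mL

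Section 2.2.4 links more than 90% platelet glutaminase inhibition to levels above 250 ng/mL (0.25 µg/mL). The estimated trough lies on either side of that, so some loss of effect at trough is possible.

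**The case against.** The strongest reply is that section 9.3 never says the test is fasted against fed. Change before and after treatment also fits Day 1 pre-dose against Day 15 pre-dose, which the schedule already supplies. That stands: the contrast is undefined, and the confounded reading is an inference from the 0–8 hour window. It does not remove the need to name the samples.

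Second, section 2.2.4 reports a 1.5- to 2-fold rise in plasma glutamine at C1D15 in all dose groups. Those groups include three-times-daily dosing, which section 2.2.5 describes as fasted. A reader might infer from the sensitivity table that a meal could account for the whole glutamine signal. The documents do not support that: they give no meal effect, and this result points to a real drug effect on glutamine. No matching plasma figure is given for glutamate or aspartate, so those tests are not covered.

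Third, a reader might infer that the meal also biases the comparison of metabolite change with response. A shift common to all patients cannot, and nothing in the documents suggests that meal response differs between responders and non-responders.

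Fourth, the patient diary (Appendix G) says the C1D1 and C1D15 morning doses are taken fasting. This contradicts sections 5.1, 5.4.5.4 and 11. Until it is reconciled, the food state of the post-dose samples is uncertain and may vary between patients.

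Finally, the stakes are limited. This is a correlative endpoint, and no stopping or success rule in section 9.1 uses it.

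**Conclusion.** The point holds in this form. Section 9.3, item 3, leaves its contrast undefined. If the body text on sampling is followed, the contrast its window suggests estimates drug plus meal and cannot alone support a claim of glutaminase inhibition. The same applies to fasted baseline against fed Week 4 in 1.3.4. The size of the effect cannot be derived from the documents. The 17% to 52% rejection rates at n = 27 rest on an assumed shift of 0.2 to 0.4 SD and no drug effect; they show sensitivity, not an estimated bias. The stated power is correct, and the rank-sum and ROC analyses are not biased by a common shift. Confidence is moderate, because the time points are not named and the diary conflicts with the body text.

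**What to change.** - In section 9.3, item 3, name fasted Day 1 pre-dose versus fasted Day 15 pre-dose as a formal signed-rank contrast, and rest any statement that the change is due to drug alone on it.
- Keep the 0–8 hour post-dose change as a peak-effect analysis. Name its day and time points, and label it as drug plus meal.
- State which of the two changes enters the rank-sum and ROC analyses.
- For 1.3.4, keep the one-month sample, state that fasted screening versus fed Week 4 includes a meal effect, and report the fasted Day 1/Day 15 pair beside it.
- Reconcile Appendix G with sections 5.1, 5.4.5.4 and 11 on food state at the C1D1 and C1D15 morning doses.

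The cost is wording: both fasted samples are already scheduled. The downside is that Day 15 pre-dose is a trough, about 12 hours after the last dose with a half-life of about 4 hours. It may understate peak inhibition and have less power (52% at n = 27 if the effect is 0.4 SD). That is why the post-dose analysis should stay alongside it.
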